## **Study population and methods**

### **Design**

A randomized open label, interventional study in 60 patients investigating if treatment with zoledronic acid prevents bone loss after denosumab treatment when administrated six (6-month group, n=20) or nine months (n=20, 9-month

group) after last injection of denosumab or when bone turnover is increased (n=20, observation group). Forty patients will be allocated to the two intervention groups and 20 patients will be followed without treatment for up to 12 months after the last denosumab treatment. The patients in the observation group and the nine months group will be monitored monthly and if p-carboxy-terminal collagen crosslinks (p-CTX) increases above 1.26µg/l (50% above the normal range for postmenopausal women and elderly men) infusion of zoledronic acid will be administered. Furthermore, a DXA scan (lumbar spine and hip sites) will be performed after three months in the observation group. If BMD has decreased more than 5% at the lumbar spine or total hip, infusion of zoledronic acid will be administered. Finally, if a patient in the 9 months group or the in the observation group suffers an osteoporotic clinical vertebral or hip fracture, infusion of zoledronic acid will be administered.

The patients will be given a single infusion of zoledronic acid as the increase in bone turnover seen after stopping denosumab seems most prominent in the first year [12]. The patients will be monitored with DXA 6, 12 and 24 months after the infusion of zoledronic acid. Zoledronic acid will be re-administered if BMD has decreased more than 5% at the lumbar spine, total hip or femoral neck.

If p-CTX increases above 1.26 µg/l during the 2nd year a second infusion of zoledronic acid will be administered.

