### **Randomization**

The patients will be randomized to infusion of zoledronic acid administered either six (6-month-group, n=20) or nine months (9-month group, n=20) after the last denosumab injection or to observation in the form of monthly monitoring of bone resorption (observation group, n=20). If p-CTX increases above 1.26 ug/l in patients in the observation group or the nine months group, zoledronic acid will be administered. If BMD decreases by more than 5% at any site after three months in the observation group, infusion of zoledronic acid will be administered.

The randomization code will be generated by the hospital pharmacy, Aarhus University Hospital. Participants will be randomized in blocks of 6.

---

 In case of dropouts the randomization codes will be reused. The codes will be randomized amongst the new participants.

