### **Recruitment of participants**

The patients will be recruited from the outpatient clinics and the DXA units to which patients are referred from their general practitioner at:

Department of Endocrinology and Internal Medicine  
Aarhus University Hospital

Possible participants will be approached during visits or by letter. Patients with osteoporosis living in the Central Region of Denmark, who have redeemed five or six prescriptions for denosumab in the last three years, will be approached by letter. All staff at the outpatient clinics will be informed about the study including inclusion and exclusion criteria. If the patient is interested in receiving further information, he or she will receive written information about the project. Moreover, we will advertise in daily newspapers and on the webpages [www.forsogsperson.dk](http://www.forsogsperson.dk) and [www.sundhed.dk](http://www.sundhed.dk). Participants who respond to advertisements will be sent written information. Subsequently, all possible participants will be invited to a meeting to obtain oral information from one of the investigators. Family members or friends are welcome to participate in the meeting as well. Afterwards the possible participant will be given 14 days to consider whether they wish to participate in the study or not, before they sign the consent form. The participants will not take part in the study before the consent form has been signed.

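### A fixed block size of 6, written in the protocol of an open-label trial with one recruiting department, lets staff who track allocations know up to about one in five in advance

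*Combined protocol and SAP*

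**What the plan says.** The Design section describes "A randomized open label, interventional study in 60 patients", with 20 patients in each of three arms. The Randomization section states "The randomization code will be generated by the hospital pharmacy, Aarhus University Hospital" and then "Participants will be randomized in blocks of 6". It mentions neither varying block sizes nor stratification. Nothing in the document says how an allocation is concealed, at what point between consent and baseline it is released, or whether the block size is withheld from recruiting staff.

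Footnote 4 to the same section adds: "In case of dropouts the randomization codes will be reused". Its next sentence says that the reused codes are shuffled among the replacement patients. Under Statistical analysis and power calculation, replacement begins once four patients in all have dropped out.

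Recruitment of participants lists one department, and "all possible participants will be invited to a meeting to obtain oral information from one of the investigators". The people who talk to candidates therefore work from the document that names the block size.

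**The concern.** Concealment means that nobody deciding whether or when to enrol a patient can foresee the arm. A constant, known block size weakens this even if the list itself is perfectly hidden. Open treatment reveals each past allocation, and the balance within the block then gives away some of the remaining ones.

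There is a plausible motive here. Zoledronic acid is given on day 0, at month 3, or by month 6 at the latest, depending on the arm. The protocol's own ethics section discusses vertebral fractures following withdrawal of denosumab. An investigator who foresees observation for a worrying patient could hold that patient back or enrol someone else first.

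If that happened, bone turnover and fracture risk at entry could differ between arms. The exposed analyses are the between-group ones: the chi-square test on the co-primary failure proportion and the mixed models for BMD change. The planned per-protocol analysis would not correct an imbalance present at entry.

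**Working it through.** **The plan's own figures.** The plan gives no figure for predictability. Its between-group sample size reproduces: 2 × (1.960 + 0.842)² × 3² / 3² = 15.7, so 16 per group. The block size does not affect it.

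**Inputs.** Block size 6 and three arms of 20 (Randomization); open label and 60 patients (Design); one department (Recruitment of participants). Equal arms imply two places per arm per block, and 60 / 6 = 10 complete blocks. Assumptions: one unstratified list, and staff who follow every earlier allocation in order.

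**Enumeration.** A block has 6! / (2! 2! 2!) = 90 possible orders. An allocation is certain when only one arm has places left.

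- Positions 1 to 4: at least three places remain and no arm holds more than two, so at least two arms are possible. Never certain.
- Position 5: certain when the last two places belong to one arm, which is 3 of C(6,2) = 15 pairs, or 1/5.
- Position 6: always certain.

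| Position | Certain | At least one arm ruled out | Best guess correct |
|---|---|---|---|
| 1 | 0 | 0 | 1/3 |
| 2 | 0 | 0 | 2/5 |
| 3 | 0 | 1/5 | 1/2 |
| 4 | 0 | 3/5 | 8/15 |
| 5 | 1/5 | 1 | 3/5 |
| 6 | 1 | 1 | 1 |
| Mean over 6 | 1.2/6 = 20.0% | 2.8/6 = 46.7% | 3.367/6 = 56.1% |

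The best guess names the arm with most places left; chance is 33.3%.

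**In 60 patients.** 0.20 × 60 = 12 certain allocations expected. The minimum is 10 (only the sixth place in each block) and the maximum 20 (the fifth as well in every block). By symmetry 12 / 3 = 4 of these are to observation, or 4/60 = 6.7% of the trial.

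**Replacement codes.** Staff know which arms the dropouts left, so they know the contents of the pool. Shuffling hides the order, but the last code is always deducible. If four codes are pooled and all are used, at least 1 of 4 is certain; if all four came from one arm, all are.

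**Alternatives.** A fixed block of 9 gives 1/7 = 14.3% certain (8.6 of 60), and a fixed block of 12 about 11%. For sizes drawn at random, 4,000 lists were simulated per set, with a recruiter who knows the possible sizes but not their order:

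- {3, 6}: 8.6%
- {6, 9}: 5.1%
- {3, 6, 9}: 3.6%, about 2 of 60
- {6, 9, 12}: 2.4%

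These lists were cut at 60 rather than made to total exactly 60. Holding each arm at exactly 20 leaves the very last places deducible under any scheme: a single block of 60 still gives about 2.5%, or 1.5 patients.

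**The case against.** A fixed permuted block with a code generated by a pharmacy is a recognised method, and the plan contains no contradiction here. That stands: this is a design choice that could be better, not an error.

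The room for steering is also limited. Several eligibility criteria are objective (T-score, eGFR, fracture history), and excluding patients with any low-energy vertebral fracture or a T-score below -2.5 removes many of those an investigator might most want to protect. Baseline is tied to the injection date, because the 6-month arm is infused on day 0. Candidates have 14 days to consider. At the planned rate of 60 in 12 months, or 5 a month, about 5 × 14/30 = 2.3 others would enrol meanwhile, so the block position at first approach is often not the position at allocation. These points reduce the opportunity but do not close it. Eligibility requires an injection less than five months earlier while day 0 falls at six months, and the plan does not say when in that interval the code is drawn.

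The sample size of 20 rests mainly on a within-group test, and between-group analyses of BMD are called exploratory. That lowers the stakes, but the failure proportion is a co-primary endpoint compared between arms.

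A reader might infer that public posting of the block size informed recruiters. The documents do not support this: this version is dated 29 January 2018, and the planned recruitment window was November 2016 to October 2017. The mechanism is that investigators hold the protocol, and whether the version used during recruitment named the block size cannot be checked here.

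**Conclusion.** The point holds as a weakness in concealment of low severity with a cheap remedy. With full tracking, an expected 20% of the initial 60 allocations are known in advance, and best guesses are right 56% of the time rather than 33%. These figures are exact for one unstratified list with two places per arm per block. That staff track every allocation is an inference from open treatment, one listed department and recruitment by the investigators; less tracking gives less foreknowledge.

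Three stronger readings are tempting and not supported:

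- That the arms would be unbalanced. The documents show an opportunity and a plausible motive, not that selection occurred, and they give no basis for sizing a bias in BMD or failure.
- That one patient in five could be steered away from observation. Only about 4 of the 12 certain allocations are to that arm.
- That reuse of dropouts' codes simply exposes them. Footnote 4 shuffles them among replacements; what remains deducible is the last code in the pool, and more only if the dropouts cluster in one arm.

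**What to change.** **For any remaining or replacement enrolment.** Have the hospital pharmacy prepare the list with randomly varying block sizes in multiples of 3 that total the planned number. Keep the sizes out of the protocol held at the site. State in the Randomization section that each allocation is released only after consent and baseline data are recorded. The cost is a new list from the same pharmacy and a short protocol change. The downside is a slightly larger temporary imbalance during accrual. The sample size does not change.

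**If recruitment is already complete.** A new list cannot help. Report the concealment and release procedure actually used, who knew the block size, and how replacement codes were issued. Then examine baseline balance by block position: compare baseline BMD, bone turnover markers and age between arms separately for positions 5 and 6 and for positions 1 to 4, with replacement patients shown apart. With 60 patients this check has little power, so an unremarkable result does not prove that there was no selection. Interpret the between-group comparisons accordingly. This costs one table and a paragraph in the report.

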### **Statistical analysis and power calculation**

Baseline characteristics of the three groups will be presented using descriptive analysis and compared using ANOVA and post-hoc unpaired t-tests if ANOVA demonstrates differences between the groups. Changes in bone mineral density one year after the zoledronic acid infusion within groups will be investigated using paired-sample t-tests and compared with the changes reported after stopping denosumab after two years [12] for the three groups combined and individually using one-sample t-test. The proportion of patients who fails to maintain BMD will be compared between groups using chi-sq test. Changes in bone mineral density, HRpQCT measures and markers of bone turnover will be compared between groups using mixed model analysis. Exploratory analyses will include multiple regression analyses aiming at identifying baseline factors or changes occurring at three or six months, which affect the change in BMD one year after the zoledronic acid infusion. Factors included in this analysis will be gender, age, years of treatment with denosumab, baseline BMD, baseline bone turnover markers, change in bone turnover markers three and six months after the zoledronic acid infusion.

Based on a previous study a 5% decrease in lumbar spine BMD can be expected during the first year after discontinuation with a 3% standard deviation [12]. The hypothesis is that treatment with zoledronic acid can decrease this bone loss. Eighteen patients will be needed to demonstrate a bone loss  $\geq 2.5$  % using a paired-sample t-test with a power of 90% and level of significance of 5%. If the decrease is less than that BMD is maintained and the hypothesis can be accepted. To account for dropouts n is increased to 20 in each group. As comparisons between the different treatment regiments suggested in this protocol never have been done before, we cannot estimate differences between groups. However, the least significant change in lumbar spine BMD using DXA is 3%. The SD of lumbar spine BMD in our facility is 3% [18]. To be able to demonstrate a difference in change in lumbar spine BMD between the three groups equal to the least significant change using independent samples t-test we need 16 patients in each group with a standard

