deviation of 3%, power of 80% and significance level of 5%. Thus, the already planned 20 participants per group are sufficient to make meaningful exploratory analyses. New participants will be enrolled after four dropouts in total. Per-protocol analysis will be performed.

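### Replacement patients receive the recycled codes of known dropouts in an open-label trial, so their allocation is easier to predict than allocation from the main list

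*Combined protocol and SAP*

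**What the plan says.** The Design section describes "A randomized open label, interventional study in 60 patients". The Randomization section allocates patients to infusion "either six (6-month-group, n=20) or nine months (9-month group, n=20) after the last denosumab injection or to observation", with 20 in each of the three groups. It states that "The randomization code will be generated by the hospital pharmacy, Aarhus University Hospital" and that "Participants will be randomized in blocks of 6". The footnote to the block size gives the rule for dropouts: "In case of dropouts the randomization codes will be reused. The codes will be randomized amongst the new participants".

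The section Statistical analysis and power calculation sets the trigger, "New participants will be enrolled after four dropouts in total", and the analysis set, "Per-protocol analysis will be performed".

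The documents do not say:
- who holds the list after it is generated, or who reassigns returned codes;
- whether returned codes are released as a batch or singly;
- whether eligibility and consent must be recorded before a code is released.

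**The concern.** A replacement does not take the next place on an unknown list. It takes one of the codes left behind by patients who withdrew. The arm of each of those patients was visible, because one group is infused at the start, another is scheduled for month 3, and the third is monitored. Staff who know who left therefore know which arms are on offer. As codes are used up, they increasingly know which arm comes next.

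Whoever approaches or enrols a replacement could then let the expected arm influence the choice of patient. A motive is plausible: Safety and ethical considerations discusses vertebral fractures after stopping denosumab and describes safeguards for patients not infused at once. Selection of this kind would affect the between-group comparisons of BMD change and of the proportion failing to maintain BMD, the latter being a co-primary endpoint. An arm that loses more patients also receives more of these replacements. If the per-protocol set leaves out the dropouts and counts their replacements, the comparison moves further from the groups first randomised.

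**Working it through.** The plan gives no figure for predictability, so there is none to reproduce. Its within-group sample size does reproduce: a 2.5% loss, SD 3%, two-sided 5% and 90% power in a paired t-test (noncentral t) give 17.2, so 18. The sidedness is assumed, as the plan does not state it.

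**Inputs.** Three equal arms and blocks of 6 (Randomization). Returned codes are shuffled among new participants (footnote to Randomization). Arms are visible (Design). Two assumptions are added: each dropout comes from each arm with probability 1/3, and four codes are returned together.

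**Measures.** An allocation is *certain* if all codes still in the pool belong to one arm. The *best guess* names the most frequent remaining arm and is right with probability (largest remaining arm count) / (remaining codes).

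**Batch of four.** With k codes left, all are from one arm with probability (1/3)^(k−1). Expected certain allocations = 1 + 1/3 + 1/9 + 1/27 = 40/27 = 1.48 of 4, or 37%.

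By how the four dropouts fall over the arms (81 equally likely ordered sets):

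| Split | Sets | Certain, of 4 | Correct guesses, of 4 |
|---|---|---|---|
| 2/1/1 | 36 | 1.17 | 2.58 |
| 2/2/0 | 18 | 1.33 | 2.83 |
| 3/1/0 | 24 | 1.75 | 3.25 |
| 4/0/0 | 3 | 4 | 4 |

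Weighted correct guesses = (36×2.583 + 18×2.833 + 24×3.25 + 3×4)/81 = 2.89 of 4, or 72%. In (18 + 24 + 3)/81 = 56% of batches at least one arm is not on offer at all.

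**Comparator: the main list in blocks of 6 (2:2:2).** The sixth allocation is always certain, and the fifth is certain if the last two codes match (probability 1/5). So (1 + 1/5)/6 = 20% are certain. The best-guess rate by the same enumeration is 56%.

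**Other batch sizes.**

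| Codes returned together | Certain | Correct guess |
|---|---|---|
| 1 (one-for-one reuse) | 100% | 100% |
| 2 | 67% | 83% |
| 3 | 48% | 77% |
| 4 | 37% | 72% |
| 6 | 25% | 66% |

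Even six recycled codes are more predictable than a block of 6.

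**Reach.** Four replacements are 4/64 = 6% of those randomised. If all four entered one arm they would be 4/20 = 20% of it.

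**The case against.** Much of the case against this point is fair.

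- **Not every allocation is known.** A reader might infer that staff know each replacement's arm in advance. The documents do not support that: the footnote shuffles the returned codes, which hides the order when several arms are pending. The 37% is an average under an assumed batch of four. That recruiting staff know who left, and from which arm, is inferred from open-label conduct and not stated.
- **Chance is not the right comparator.** It is tempting to set 72% against the 33% of a pure guess. The main list is itself predictable in an open-label trial with a disclosed block size, so the excess due to the footnote is 72 − 56 = 16 points in correct guesses and 37 − 20 = 17 points in certain allocations.
- **No endpoint bias is shown.** Suppose, purely as an illustration, that each replacement's BMD change differs by a full SD (3%). One replacement in an arm of 20 shifts its mean by 3/20 = 0.15 points, and four in one arm shift it by 0.6, against the 3% between-group difference used for sizing. The main power calculation is within-group, and the plan calls the between-group BMD sizing exploratory. The failure proportion, however, is co-primary and is compared between groups.
- **Room for selection is limited.** Recruitment also runs through register-based letters and advertisements, and the exclusion of vertebral fracture and of low T-scores narrows the range of risk among candidates.
- **The trigger is not a serious fault.** A reader might object that a pooled count of four does not match the allowance of two per group ("To account for dropouts n is increased to 20 in each group"). The consequence is trivial: within-group power is 91.5% at 18 and 89.7% at 17. Four dropouts in total cannot take any arm below 16, which is the plan's own figure for the between-group comparison.

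These arguments limit the size of the problem. They do not remove it, because nothing in the documents conceals the composition of the recycled pool. Varying the block size would not conceal it either.

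**Conclusion.** The point holds as a modest and avoidable weakness in allocation concealment. Followed as written, the footnote makes replacement allocations more predictable than those on the main list: 37% certain and 72% guessed for a batch of four, against 20% and 56%. Over the batch sizes examined, the range runs from 25% and 66% (six codes) to 100% and 100% (one-for-one reuse). The figures assume equal dropout across arms and staff who know which patients left. More uneven dropout would raise them.

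The documents do not support a conclusion that the trial's results are biased. Only replacements are affected, their final number is not given, and the direction and size of any effect on BMD change or failure are unknown. The correction is still worth making, because it is cheap and the per-protocol analysis gives no protection against this selection.

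**What to change.** Replace the footnote with:

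> Randomisation codes are not reused. Additional participants receive the next unused allocation from a concealed 1:1:1 extension of the list held by the hospital pharmacy, released only after eligibility and consent are recorded.

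Keep the existing overall trigger for replacement. A per-group trigger would not fit a 1:1:1 extension. If an arm had fallen to 16, four new patients under simple 1:1:1 allocation would bring it back to 18 with probability 1 − (2/3)^4 − 4(1/3)(2/3)^3 = 33/81, about 41%. From a fresh block of 6 the probability is 6/15 = 40%.

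Under simple 1:1:1 allocation no replacement is certain and 33% are guessed. If the extension keeps disclosed blocks of 6, predictability returns to the main list's 20% and 56%. In either case it no longer depends on who dropped out.

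**Cost.** A short amendment and a longer pharmacy list. A depleted arm is no longer refilled one for one, so group sizes may end a few patients apart. If all four dropouts came from one arm and none were replaced there, within-group power at n = 16 would be 87.6%, against 91.5% at 18.

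**Timing.** The document is dated January 2018, and Research plan and facilities schedules recruitment to October 2017, so an amendment may come too late for some patients. If replacements were already enrolled under the footnote, identify them, report their number by arm, and add a sensitivity analysis without them.
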